	Sunitinib+ lanreotide	XX (XX.X%)	0 (0.0%)	XX (XX.X%)
	Sunitinib+ other	XX (XX.X%)	0 (0.0%)	XX (XX.X%)
	Chemotherapy + octreotide	XX (XX.X%)	0 (0.0%)	XX (XX.X%)
	Chemotherapy + lanreotide	XX (XX.X%)	0 (0.0%)	XX (XX.X%)
	Chemotherapy + other	XX (XX.X%)	0 (0.0%)	XX (XX.X%)

⁽¹⁾ Percentages calculated as a proportion of the number of patients concerned.

Programmer note: show all of the combinations used in patients in the study.

Table 14.1.4.1.13: Caracteristics of the Main Treatment with Targeted Therapy at Inclusion: Sunitinib – Reference Set

		Sunitinib (N=XX)
Started before the inclusion consultation	N	XX
Started Service the metasion consultation	Missing data	XX
	Yes	XX (XX.X%)
	No	XX (XX.X%)
Treatment started	N	XX
	Missing data	XX
	Monotherapy	XX (XX.X%)
	Combination	XX (XX.X%)
Treatment received – details	N	XX
	Missing data	XX
	Sunitinib alone	XX (XX.X%)
	Sunitinib + octreotide	XX (XX.X%)
	Sunitinib + lanreotide	XX (XX.X%)
	Sunitinib + other	XX (XX.X%)
Time between start of treatment and inclusion (months) (prevalent patients)	N	XX
	Missing data	XX
	Mean (SD)	XX.XX (X.XX)
	Median	XX.X
	[Min; Max]	[XX.X; XX.X]
	[Q1; Q3]	[XX.X; XX.X]
Time between start of treatment and inclusion	N	XX
(days) (incident patients)		1111
	Missing data	XX

Table 14.1.4.1.13: Caracteristics of the Main Treatment with Targeted Therapy at Inclusion: Sunitinib – Reference Set

		Sunitinib (N=XX)
	Mean (SD)	XX.XX (X.XX)
	Median	XX.X
	[Min; Max]	[XX.X; XX.X]
	[Q1; Q3]	[XX.X; XX.X]
arting dose (N(%))	N	XX
	Missing data	XX
	37.5 mg/day	XX (XX.X%)
	25 mg/day	XX (XX.X%)
	•••	XX (XX.X%)
ange in dose step since initiation in	N	XX
evalent patients		
	Missing data	XX VV (VV V0/)
	0	XX (XX.X%)
	1	XX (XX.X%) XX (XX X%)
	•••	XX (XX.X%)
me since last change in dose (days) in	N	XX
evalent patients (1)	Missing data	XX
	Mean (SD)	XX.XX (X.XX)
	Median	XX.X
	[Min; Max]	[XX.X; XX.X]
	[Q1; Q3]	[XX.X; XX.X]
pe of change of dose steps since starting		
eatment in prevalent patients (2)	N	XX
1 ()	Missing data	XX
	Increase	XX (XX.X%)
	Reduction	XX (XX.X%)
	•••	XX (XX.X%)
ose after increase in treatment in prevalent	N	N/N/
tients (2)	N	XX
	Missing data	XX
	37.5 mg/day	XX (XX.X%)
	25 mg/day	XX (XX.X%)
		XX (XX.X%)
ose after reducing treatment in prevalent	N	XX
tients (N(%)) (2)		
	Missing data 37.5 mg/day	XX XX (XX.X%)
	- ·	XX (XX.X%) XX (XX.X%)
	25 mg/day	XX (XX.X%) $XX (XX.X%)$
	•••	$\Lambda\Lambda$ ($\Lambda\Lambda.\Lambda/0$)
least one dose reduction since starting	N	XX
atment in prevalent patients	Missing data	XX
	Yes	XX XX (XX.X%)
	No	XX (XX.X%)
	110	$\Lambda\Lambda$ ($\Lambda\Lambda.\Lambda/0$)
least one dose increase since starting	N	XX
eatment in prevalent patients	Missing data	XX
	Yes	XX (XX.X%)
	No	XX (XX.X%)
	110	()
	110	()
easons for reducing dose since starting eatment in prevalent patients (2)	N	XX

Table 14.1.4.1.13: Caracteristics of the Main Treatment with Targeted Therapy at Inclusion: Sunitinib – Reference Set

		Sunitinib (N=XX)
	Adverse event	XX (XX.X%)
	Patient's choice	XX (XX.X%)
	Doctor's choice	XX (XX.X%)
	Other	XX (XX.X%)
D		
Reasons for increasing dose since starting treatment in prevalent patients (2)	N	XX
	Missing data	XX
	Adverse event	XX (XX.X%)
	Patient's choice	XX (XX.X%)
	Doctor's choice	XX (XX.X%)
	Other	XX (XX.X%)
Time between 1 st change in dose of treatment		
(days) in prevalent patients (1)	N	XX
• •	Missing data	XX
	Mean (SD)	XX.XX (X.XX)
	Median	XX.X
	[Min; Max]	[XX.X; XX.X]
	[Q1; Q3]	[XX.X; XX.X]
	[(-) (-)	[
Mean time between two changes in dose (days) in treatment in prevalent patients (2)	N	XX
(days) in treatment in prevalent patients (2)	Missing data	XX
	Mean (SD)	XX.XX (X.XX)
	Median	XX.XX
	[Min; Max]	[XX.X; XX.X]
	[Q1; Q3]	[XX.X; XX.X]
Discontinuation >7 days since start of	N	XX
treatment in prevalent patients	NO. 1 .	NA.
	Missing data	XX
	Yes	XX (XX.X%)
	No	XX (XX.X%)
Number of discontinuations prior to inclusion		N
in prevalent patients (1)		No. 1 . 1 .
		Missing data
	1	n (%)
	•••	n (%)
Time since last discontinuation of treatment (days) in prevalent patients (1)	N	XX
(y-) Pro . mone pariones (1)	Missing data	XX
	Mean (SD)	XX.XX (X.XX)
	Median	
		XX.X
	[Min; Max]	[XX.X; XX.X]
	[Q1; Q3]	[XX.X; XX.X]
Duration of discontinuations of treatment in	N	XX
prevalent patients (days) (2)	Missing data	XX
	•	
	Mean (SD)	XX.XX (X.XX)
	M - 1:	VV V
	Median	XX.X
	Median [Min; Max] [Q1; Q3]	XX.X [XX.X; XX.X] [XX.X; XX.X]

Table 14.1.4.1.13: Caracteristics of the Main Treatment with Targeted Therapy at Inclusion: Sunitinib – Reference Set

		Sunitinib (N=XX)
Reasons for discontinuations of treatment in prevalent patients (2)	N	XX
	Missing data	XX
	Adverse event	XX (XX.X%)
	Patient's choice	XX (XX.X%)
	Doctor's choice	XX (XX.X%)
	Other	XX (XX.X%)

⁽¹⁾ As a proportion of number of patients concerned.

Programmer note:

- For the variable "Treatment received", show all of the combinations listed.
- For the variable "Dose (N(%))", show all of the doses reported (including those in "Others").
- "Type of change in dose step since initiation": N=total number of changes in dose step (there may be several of these in any one patient).
- "Duration of discontinuations (days)" and "Reasons for discontinuations": N=total number of discontinuations (there may be several of these in the same patient).
- Time between the 1st change in dose = date of first change in dose date treatment was started.
- Mean time before change in dose = mean time between two different consecutive doses.

Using the same template:

Table 14.1.4.1.14: Details of the Main Treatment by Targeted Therapy at Inclusion: Everolimus – Reference Set

Programmer note: for the variables "Reasons for reduction in dose since starting", "Reasons for increase in dose since starting" and "Reasons for discontinuation" the modalities are "Adverse event related to everolimus", "Adverse event not related to everolimus", "Adverse event (relationship with everolimus not stated)", "Patient's choice" and "Doctor's choice."

⁽²⁾ As a proportion of the number of changes/increases/reductions.

Table 14.1.4.1.15: Details of the Main Treatment with Chemotherapy at Inclusion – Reference Set

		Chemotherapy (N=XX)
Started before the inclusion consultation	N	vv
Started before the inclusion consultation	N Missing data	XX
	Missing data	XX
	Yes	XX (XX.X%)
	No	XX (XX.X%)
Treatment started	N	XX
	Missing data	XX
	Monotherapy	XX (XX.X%)
	Combination	XX (XX.X%)
Treatment received	N	VV
Treatment received	N	XX
	Missing data	XX
	Chemotherapy alone	XX (XX.X%)
	Chemotherapy + somatostatin analog	XX (XX.X%)
	Chemotherapy + Other	XX (XX.X%)
Treatment received – Details	N	XX
Treatment received Details	Missing data	XX
	5FU	XX (XX.X%)
	5FU + capecitabine	XX (XX.X%)
		XX (XX.X%)
Time between start of treatment and inclusion (months) (prevalent patients)	N	XX
(months) (prevalent patients)	Missing data	XX
	Missing data	
	Mean (SD)	XX.XX (X.XX)
	Median	XX.X
	[Min; Max]	[XX.X; XX.X]
	[Q1; Q3]	[XX.X; XX.X]
Time between start of treatment and inclusion (days) (incident patients)	N	XX
(days) (meident patients)	Missing data	XX
	=	
	Mean (SD)	XX.XX (X.XX)
	Median	XX.X
	[Min; Max]	[XX.X; XX.X]
	[Q1; Q3]	[XX.X; XX.X]
Number of treatment cycles given to prevalent	N	XX
patients	Missing data	XX
	Mean (SD)	XX.XX (X.XX)
	Median	XX.XX
	[Min; Max]	[XX.X; XX.X]
	[Q1; Q3]	[XX.X; XX.X]
Number of treatment cycles given to prevalent patients $(N(\%))$	N	XX
patients (14(70))	Missing data	XX
	Missing data	XX (XX.X%)
	2	XX (XX.X%)
		XX (XX.X%)
Frequency of treatment cycles in prevalent patients	N	XX
patients	Missing data	XX
	•	
	7 days	XX (XX.X%)
	14 days	XX (XX.X%)
	•••	XX (XX.X%)

Table 14.1.4.1.15: Details of the Main Treatment with Chemotherapy at Inclusion – Reference Set

		Chemotherapy (N=XX)
Change in dose step since starting treatment in	n N	XX
prevalent patients	Missing data	XX
	0	XX (XX.X%)
	1	XX (XX.X%)
		XX (XX.X%)
	•••	727 (727.7770)
ime since last change in dose (days) of reatment in prevalent patients (1)	N	XX
1 1 ()	Missing data	XX
	Mean (SD)	XX.XX (X.XX)
	Median	XX.X
	[Min; Max]	[XX.X; XX.X]
	[Q1; Q3]	[XX.X; XX.X]
ype of change of dose step since starting	N	XX
reatment in prevalent patients (2)		
	Missing data	XX
	Increase Reduction	XX (XX.X%)
		XX (XX.X%)
	•••	XX (XX.X%)
at least one reduction in dose since starting reatment in prevalent patients	N	XX
eatment in prevaient patients	Missing data	XX
	Yes	XX (XX.X%)
	No	XX (XX.X%)
		, ,
at least one increase in dose since starting	N	XX
reatment in prevalent patients	Missing data	XX
	Yes	XX (XX.X%)
	Non	XX (XX.X%)
leasons for reduction in dose in dose since		
tarting treatment in prevalent patients (2)	N	XX
	Missing data	XX
	Adverse event	XX (XX.X%)
	Patient's choice	XX (XX.X%)
	Doctor's choice	XX (XX.X%)
	Other	XX (XX.X%)
easons for increase in dose in dose since	N	XX
tarting treatment in prevalent patients (2)		
	Missing data	XX
	Adverse event	XX (XX.X%)
	Patient's choice	XX (XX.X%)
	Doctor's choice	XX (XX.X%)
	Other	XX (XX.X%)
ime before 1st change in dose (days) of	N	XX
eatment in prevalent patients (1)		
	Missing data	XX
	Mean (SD)	XX.XX (X.XX)
	Median	XX.X
	[Min; Max] [Q1; Q3]	[XX.X; XX.X] [XX.X; XX.X]
	[41, 43]	
Mean time before change in dose (days) of	N	XX
eatment in prevalent patients (2)		
	Missing data	XX
	Mean (SD)	XX.XX (X.XX)

Table 14.1.4.1.15: Details of the Main Treatment with Chemotherapy at Inclusion – Reference Set

		Chemotherapy (N=XX)
	Median	XX.X
	[Min; Max]	[XX.X; XX.X]
	[Q1; Q3]	[XX.X; XX.X]
Time difference of at least 7 days since starting	N	VV
treatment in prevalent patients	IN	XX
·	Missing data	XX
	Yes	XX (XX.X%)
	No	XX (XX.X%)
Reasons for time differences in treatment for		
prevalent patients (2)	N	XX
()	Missing data	XX
	Adverse event	XX (XX.X%)
	Patient's choice	XX (XX.X%)
	Doctor's choice	XX (XX.X%)
	Other	XX (XX.X%)

- (1) As a proportion of the number of prevalent patients.
- (2) As a proportion of the number of patients concerned.
- (3) As a proportion of the number of changes/increases/reductions.

Programmer note:

• For the variable "Frequency of cycles", show all of the frequencies reported (including those in "Others").

Table 14.1.4.1.16: Details of the Main Treatment with Interferon Alpha at Inclusion – Reference Set

		Interferon alpha (N=XX)
Started before the inclusion consultation	N	XX
Started before the metasion consultation	Missing data	XX
	Yes	XX (XX.X%)
	No No	XX (XX.X%)
Treatment started	N	XX
	Missing data	XX
	Monotherapy	XX (XX.X%)
	Combination	XX (XX.X%)
Treatment received – Details	N	XX
	Missing data	XX
	Interferon alpha alone	XX (XX.X%)
	Interferon alpha + Somatostatin analog	XX (XX.X%)
	Interferon alpha+ Other	XX (XX.X%)
Type of treatment	N	XX
	Missing data	XX
	Pegylated	XX (XX.X%)

Table 14.1.4.1.16: Details of the Main Treatment with Interferon Alpha at Inclusion – Reference Set

		Interferon alpha (N=XX)
	Standard	XX (XX.X%)
Time between start of treatment and inclusion (months) (prevalent patients)	N	XX
(Missing data Mean (SD)	XX XX.XX (X.XX)
	Median	XX.X
	[Min; Max] [Q1; Q3]	[XX.X; XX.X] [XX.X; XX.X]
Time between start of treatment and inclusion (days) (incident patients)	N	XX
merasion (days) (meraent patients)	Missing data	XX
	Mean (SD) Median	XX.XX (X.XX) XX.X
	[Min; Max]	[XX.X; XX.X]
	[Q1; Q3]	[XX.X; XX.X]
Starting dose (N(%))	N M: 1	XX
	Missing data Mean (SD)	XX XX.XX (X.XX)
	Median	XX.X
	[Min; Max] [Q1; Q3]	[XX.X; XX.X] [XX.X; XX.X]
Change in dose step since starting treatment in prevalent patients	N	XX
in prevaient patients	Missing data	XX
	0 1	XX (XX.X%) XX (XX.X%)
		XX(XX.X%)
Time since last change in dose (days) of	N	VV
treatment in prevalent patients (1)	N Missions data	XX
	Missing data Mean (SD)	XX XX.XX (X.XX)
	Median	XX.X
	[Min; Max] [Q1; Q3]	[XX.X; XX.X] [XX.X; XX.X]
		. , ,
Reasons for change in dose since starting treatment in prevalent patients (2)	N	XX
treatment in prevalent patients (2)	Missing data	XX
	Adverse event	XX (XX.X%)
	Patient's choice Doctor's choice	XX (XX.X%) XX (XX.X%)
	Other	XX (XX.X%)
Time before 1 st change in dose (days) of treatment in prevalent patients (1)	N	XX
	Missing data	XX
	Mean (SD) Median	XX.XX (X.XX) XX.X
	[Min; Max]	[XX.X; XX.X]
	[Q1; Q3]	[XX.X; XX.X]

Table 14.1.4.1.16: Details of the Main Treatment with Interferon Alpha at Inclusion – Reference Set

		Interferon alpha (N=XX)
Mean time before change in dose (days) of treatment in prevalent patients (2)	N	XX
, F(e)	Missing data Mean (SD) Median [Min; Max] [Q1; Q3]	XX XX.XX (X.XX) XX.X [XX.X; XX.X] [XX.X; XX.X]
Time difference of at least 7 days since starting treatment in prevalent patients	N	XX
	Missing data No Yes	XX XX (XX.X%) XX (XX.X%)
Reasons for time differences in treatment for prevalent patients (2)	N	XX
(=/	Missing data	XX
	Adverse event	XX (XX.X%)
	Patient's choice	XX (XX.X%)
	Doctor's choice Other	XX (XX.X%) XX (XX.X%)

⁽¹⁾ As a proportion of the number of patients concerned.

Table 14.1.4.1.17: Details of the Main Treatment with Somatostatin Analog at Inclusion – Reference Set

		Somatostatin analog (N=XX)
Started before the inclusion consultation	N	XX
	Missing data	XX
	Yes	XX (XX.X%)
	No	XX (XX.X%)
Treatment started	N	XX
	Missing data	XX
	Monotherapy	XX (XX.X%)
	Combination	XX (XX.X%)
Treatment received	N	XX
	Missing data	XX
	Octreotide alone	XX (XX.X%)
	Octreotide + Treatment 1	XX (XX.X%)
	•••	XX (XX.X%)
Time between start of treatment and inclusion (months) (prevalent patient)s	N	XX
inclusion (months) (prevalent patient)s	Missing data	XX
	Mean (SD)	XX.XX (X.XX)
	Median	XX.X
	[Min; Max]	[XX.X; XX.X]
	[Q1; Q3]	[XX.X; XX.X]

⁽²⁾ As a proportion of the number of changes/increases/reductions.

Table 14.1.4.1.17: Details of the Main Treatment with Somatostatin Analog at Inclusion – Reference Set

		Somatostatin analog (N=XX)
Time between start of treatment and	N	XX
inclusion (days) (prevalent patients)		
	Missing data	XX
	Mean (SD) Median	XX.XX (X.XX) XX.X
	[Min; Max]	[XX.X; XX.X]
	[Q1; Q3]	[XX.X; XX.X]
Dose of octreotide (N(%))	N	XX
	Missing data	XX
	10 mg/28d	XX (XX.X%)
	20 mg/28d	XX (XX.X%)
		XX (XX.X%)
Dose of lanreotide (N(%))	N	XX
	Missing data	XX
	60 mg/28d	XX (XX.X%)
	90 mg/28d	XX (XX.X%)
	•••	XX (XX.X%)
Change in dose step since starting treatment in prevalent patients	N	XX
in prevalent patients	Missing data	XX
	0	XX (XX.X%)
	1	XX (XX.X%)
		XX (XX.X%)
Time before 1st change in dose (days) of	N	XX
treatment in prevalent patients (1)	Missing data	XX
	Mean (SD)	XX.XX (X.XX)
	Median	XX.X
	[Min; Max]	[XX.X; XX.X]
	[Q1; Q3]	[XX.X; XX.X]
Reasons for change in dose since starting		
treatment in prevalent patients (2)	N	XX
,	Missing data	XX
	Adverse event	XX (XX.X%)
	Patient's choice	XX (XX.X%)
	Doctor's choice	XX (XX.X%)
Time before 1st change in dose (days) of	Other	XX (XX.X%)
treatment in prevalent patients (1)	N M: : 1.4	XX
	Missing data Mean (SD)	XX XX.XX (X.XX)
	Median	XX.XX (X.XX) XXX.X
	[Min; Max]	[XX.X; XX.X]
	[Q1; Q3]	[XX.X; XX.X]
Mean time before change in dose (days) of	N	XX
		1111
treatment in prevalent patients (2)	M:: 1-4	3737
treatment in prevalent patients (2)	Missing data	XX VV VV (V VV)
treatment in prevalent patients (2)	Mean (SD)	XX.XX (X.XX)
treatment in prevalent patients (2)		

Table 14.1.4.1.17: Details of the Main Treatment with Somatostatin Analog at Inclusion – Reference Set

		Somatostatin analog (N=XX)
Time difference of at least 7 days since starting treatment in prevalent patients	N	XX
	Missing data	XX
	Yes	XX (XX.X%)
	No	XX (XX.X%)
Reasons for time differences in treatment for prevalent patients (2)	N	XX
,	Missing data	XX
	Adverse event	XX (XX.X%)
	Patient's choice	XX (XX.X%)
	Doctor's choice	XX (XX.X%)
	Other	XX (XX.X%)

⁽¹⁾ As a proportion of the number of patients concerned.

Table 14.1.4.1.18: Details of the Main Treatment by Metabolic Radiotherapy at Inclusion – Reference Set

		Metabolic radiotherapy (N=XX)
Started before the inclusion consultation	N	XX
	Missing data	XX
	Yes	XX (XX.X%)
	No	XX (XX.X%)
Treatment started	N	XX
	Missing data	XX
	Monotherapy	XX (XX.X%)
	Combination	XX (XX.X%)
Treatment received	N	XX
	Missing data	XX
	Metabolic radiotherapy alone	XX (XX.X%)
	Metabolic radiotherapy + somatostatin analog	XX (XX.X%)
	Metabolic radiotherapy + other	XX (XX.X%)
Time between start of treatment and	N	XX
inclusion (months) (prevalent patients)	IN	AA
	Missing data	XX
	Mean (SD)	XX.XX (X.XX)
	Median	XX.X
	[Min; Max]	[XX.X; XX.X]
	[Q1; Q3]	[XX.X; XX.X]
Time between start of treatment and	N	XX
inclusion (days) (incident patients)		
	Missing data	XX
	Mean (SD)	XX.XX (X.XX)
	Median	XX.X
	[Min; Max]	[XX.X; XX.X]
	[Q1; Q3]	[XX.X; XX.X]

⁽²⁾ As a proportion of the number of changes/increases/reductions.

Table 14.1.4.1.18: Details of the Main Treatment by Metabolic Radiotherapy at Inclusion – Reference Set

		Metabolic radiotherapy (N=XX)
Place of treatment	N	XX
	Missing data	XX
	France	XX (XX.X%)
	Netherlands	XX (XX.X%)
	Switzerland	XX (XX.X%)
	Other	XX (XX.X%)
Number of courses since start of treatment in prevalent patients	N	XX
in prevalent patients	Missing data	XX
	Mean (SD)	XX.XX (X.XX)
	Median	XX.X
	[Min; Max]	[XX.X; XX.X]
	[Q1; Q3]	[XX.X; XX.X]
Number of courses since start of treatment	N	XX
in prevalent patients (N(%))	Missing data	XX
	1	XX (XX.X%)
	2	XX (XX.X%)
		XX (XX.X%)
		· ·
Radio-isotope	N	XX
	Missing data	XX
	Lutetium	XX (XX.X%)
	Indium	XX (XX.X%)
	Yttrium	XX (XX.X%)

Listing 14.1.4.1.7: Other Reasons for Changing or Temporarily Discontinuing
Treatment at Inclusion – Reference Set

Patient Sex Age	Group	Subgroup	Change/Temporary discontinuation	Other reasons
XXXXX XXXXX XX	xxxx	xxxxxx	xxxxxxx	xxxxxx

9.1.4.2. Description of Doctors

Table 14.1.4.2.1: Characteristics of Participating Doctors

		Total (N=XX)
Specialty	N	XX
	Missing data Oncology	XX XX (XX.X%)
	Gastroenterology	XX (XX.X%)
	Endocrinology	XX (XX.X%)
	Other	XX (XX.X%)
Type of practice	N	XX
31 1	Missing data	XX
	Public	XX (XX.X%)
	Private	XX (XX.X%)
Type of facility*	N	XX
	Missing data	XX
	Hospital	XX (XX.X%)
	Primary care/clinic	XX (XX.X%)
	Cancer Centre	XX (XX.X%)
Estimated number of patients suffering from a		
pancreatic neuroendocrine tumour (treated at the time the participation agreement was completed)	N	XX
1 /	Missing data	XX
	Mean (SD)	XX.XX (X.XX)
	Median	XX.X
	[Min; Max]	[XX.X; XX.X]
	[Q1; Q3]	[XX.X; XX.X]

^{*} Several answer options are possible.

9.1.4.3. Representativeness of the Samples of Patients and Doctors

Table 14.1.4.3.1: Representativeness of Sample of Doctors

		Active doctors (N=XX)	Inactive doctors (N=XX)	Standardised difference*
Specialty	N	XX	XX	
-p	Missing data	XX	XX	
	Oncology	XX (XX.X%)	XX (XX.X%)	XX.X
	Gastroenterology	XX (XX.X%)	XX (XX.X%)	XX.X
	Endocrinology	XX (XX.X%)	XX (XX.X%)	XX.X
	Other	XX (XX.X%)	XX (XX.X%)	XX.X
Type of practice	N	XX	XX	
31 1	Missing data	XX	XX	
	Public	XX (XX.X%)	XX (XX.X%)	XX.X
	Private	XX (XX.X%)	XX (XX.X%)	XX.X
Type of facility	N	XX	XX	
- 5	Missing data	XX	XX	
	Hospital	XX (XX.X%)	XX (XX.X%)	XX.X
	Primary care/clinic	XX (XX.X%)	XX (XX.X%)	XX.X
	Cancer Centre	XX (XX.X%)	XX (XX.X%)	XX.X

Table 14.1.4.3.1: Representativeness of Sample of Doctors

		Active doctors (N=XX)	Inactive doctors (N=XX)	Standardised difference*
Estimated number of patients suffering from a pancreatic neuroendocrine tumour (treated at the time the participation agreement was completed)	N	XX	XX	
1 /	Missing data Mean (SD) Median [Min; Max] [Q1; Q3]	XX XX.XX (X.XX) XX.X [XX.X; XX.X] [XX.X; XX.X]	XX XX.XX (X.XX) XX.X [XX.X; XX.X] [XX.X; XX.X]	XX.X

^{*} Standardised difference: rapid interpretation: 0.2-0.3: weak, 0.3-0.8: moderate, >0.8: strong.

Table 14.1.4.3.2: Representativeness of Sample of Patients: Comparison of Non-Included and Included Patients

		Non-included patients* (N=XX)	Included patients (N=XX)	Standardised difference**
Age at inclusion (years)	N	XX	XX	
rige at increasion (years)	Missing data	XX	XX	
	Mean (SD)	XX.XX (X.XX)	XX.XX (X.XX)	XX.X
	Median	XX.X	XX.X	
	[Min; Max]	[XX.X; XX.X]	[XX.X; XX.X]	
	[Q1; Q3]	[XX.X; XX.X]	[XX.X; XX.X]	
Sex	N	XX	XX	
	Missing data	XX	XX	
	Male	XX (XX.X%)	XX (XX.X%)	XX.X
	Female	XX (XX.X%)	XX (XX.X%)	XX.X
Reason for non-inclusion	N	XX		
reason for non metasion	Missing data	XX		
	Patient refusal	XX (XX.X%)		
	Other	XX (XX.X%)		

^{*} data collected in the non-inclusion register.

Listing 14.1.4.3.1: Other Reasons for Non-Inclusion – Non-Included Patients

Centre No.	Registration no.	Age	Sex	Others reasons for non- inclusion
XXXXX	1	XXXXX	XXXXX	XXXXX
	2	XXXXX	XXXXX	XXXXX

^{***} Standardised difference: rapid interpretation: 0.2-0.3: weak, 0.3-0.8: moderate, >0.8: strong.

Table 14.1.4.3.3: Representativeness of the Samples of Patients: Comparison of Patients Lost to Follow-Up and/or Who Discontinued the Study Treatment Early (For a Reason Other than Death) and Patients with Full Follow-Up

		Patients lost to follow-up and/or dropped out of the study (for reason other than death) (N=XX)	Patients with complete follow- up** (N=XX)	Standardised difference*
Age at inclusion (years)	N Missing data	XX XX	XX XX	
	Missing data Mean (SD)	XX.XX (X.XX)	XX.XX (X.XX)	XX.X
	Median	XX.XX (X.XX) XX.X	XX.X XX.X	AA.A
	[Min; Max]	[XX.X; XX.X]	[XX.X; XX.X]	
	[Q1; Q3]	[XX.X; XX.X]	[XX.X; XX.X]	
Sex	N	XX	XX	
	Missing data	XX	XX	
	Male	XX (XX.X%)	XX (XX.X%)	XX.X
	Female	XX (XX.X%)	XX (XX.X%)	XX.X
ECOG index at inclusion	N	XX	XX	
	Missing data	XX	XX	
	0	XX (XX.X%)	XX(XX.X%)	XX.X
	1	XX (XX.X%)	XX (XX.X%)	XX.X
	2	XX (XX.X%)	XX (XX.X%)	XX.X
	3	XX (XX.X%)	XX (XX.X%)	XX.X
	4	XX (XX.X%)	XX (XX.X%)	XX.X
Group	N	XX	XX	
	Missing data	XX	XX	
	Targeted therapies	XX (XX.X%)	XX (XX.X%)	XX.X
	Other treatments	XX (XX.X%)	XX (XX.X%)	XX.X

The ECOG data = unknown entries were deemed to be missing data.

^{*} Standardised difference rapid interpretation: 0.2-0.3: weak, 0.3-0.8: moderate, >0.8: strong.

^{**} Patients who have complete follow-up (followed up until disease progression, death, end of main treatment ongoing at the time of inclusion or 2-year cutoff date).

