9.1.2. Patients lost to follow up during the study

There will be a particular focus on patients who leave the study, or who the investigator does not see again for a visit due to the observational nature of the study (the frequency of visits for patient follow-up can vary from one doctor to another). For patients who are lost to follow-up, a last visit/anticipated end of study questionnaire will be completed by the investigator. The statistical analyses will compare the characteristics of the enrolled patients who participate in the whole duration of the study with the enrolled patients who were later lost to follow-up and/or left the study.

[figure not shown]

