4.3. Analysis Sets

4.3.1. Patient Sets

- Non-included patients: all patients who are not included in the study (as recorded in the non-inclusion register).
- Included patients: all patients included in the study.
- Safety analysis set: all patients included in the study who received at least one dose of the documented treatment (the treatment start date must be entered) in the study (targeted therapy or other treatment). If the patient is prevalent, the treatment must

still be ongoing at the time of inclusion in the study and if the patient is incident, the treatment must be started at or after inclusion in the study.

• Reference set (Full Analysis Set): patients included who meet the eligibility criteria and have received at least one dose of the treatment documented during the prospective follow-up period (the treatment start date must be completed and the treatment stop date must be after the date of inclusion if the start date is prior to the date of inclusion) in the study (targeted therapy or other treatment). Patients with no follow-up data will be excluded from this population.

Two treatment groups will be analysed: the "targeted therapy" with two subgroups, everolimus (AFINITOR®) and sunitinib (SUTENT®); and an "other treatments" group with four subgroups: chemotherapy, somatostatin analogs, interferon-alpha and metabolic radiotherapy.

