5.4.3. Representativeness of Samples of Doctors and Patients

Comparisons will be made between active doctors who took part in the study (who included at least one patient) and inactive doctors who did not include any patients, by calculating standardised differences.

These standardised differences will be calculated as follows:

Type of variable	Equation			
Qualitative	$d = \frac{P_1 - P_2}{\sqrt{\frac{P_1(1 - P_1) + P_2(1 - P_2)}{2}}}$			
	P ₁ : proportion of individuals with the feature in group 1			
	P ₂ : proportion of individuals with the feature in group 2			
Quantitative	$d = \frac{\text{moy}_1 - \text{moy}_2}{\sqrt{\frac{\text{var}_1 + \text{var}_2}{2}}}$			
	mean ₁ : mean in group 1			
	mean ₂ : mean in group 2			
	var ₁ : variance in group 1			
	var ₂ : variance in group 2			

Similarly, comparisons will be made between included and non-included patients based on information collected in the non-inclusion register (age, sex), The reasons for non-inclusion will be presented. The "others" reasons for non-inclusion will be listed.

In addition, patients who are lost to follow-up and/or dropped out of the study (for a reason other than death) will be compared to patients with complete follow-up (follow-up until progression, death, end of main treatment ongoing at the time of inclusion or 2-year cutoff date) in the reference set.

We will deem the observed difference to be small if the standardised difference is between [0.2 and 0.3], average if between [0.3-0.8] and large if it is over 0.8. A value of 0.2 or less will be considered to represent no difference.

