6.1.2. Patients Lost to Follow-up During the Follow-up Period

Particular attention will be paid to patients who stop the study or whom the investigator does not review in a visit because of the observational nature of the study (visit frequency for patient follow-up may vary depending on the doctor). For patients who are lost to follow up, an early last news/end of study questionnaire will be completed by the investigator. The statistical analyses will compare the characteristics of included patients who participated throughout the duration of the study with those patients who were included but were lost to follow-up and/or stopped the study.

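### The comparison of lost with fully followed patients is run in a set that has already dropped patients with no follow-up data, so selective early loss can be missed

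*SAP*

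**What the plan says.** SAP 5.4.3 plans to compare patients lost to follow-up or dropped out, for reasons other than death, with patients whose follow-up is complete. Complete means followed to progression, death, "end of main treatment ongoing at the time of inclusion or 2-year cutoff date) in the reference set". Results are standardised differences, and a value of 0.2 or less is read as no difference. The template is Table 14.1.4.3.3 in SAP 9.1.4.3. Its lost column is headed "Patients lost to follow-up and/or dropped out of the study (for reason other than death", and its rows are age, sex, ECOG at inclusion and treatment group. The table title names no analysis set; the restriction comes from SAP 5.4.3.

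SAP 4.3.1 defines the reference set and ends: "Patients with no follow-up data will be excluded from this population". It does not say what counts as follow-up data.

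Two other places describe the comparison more widely. Protocol 9.1.2 sets patients who complete the study against "the enrolled patients who were later lost to follow-up and/or left the study". SAP 6.1.2 makes the comparison "with those patients who were included but were lost to follow-up and/or stopped the study". Protocol 8.3.1.2 plans the same comparison and names no analysis set. SAP 5.8, which lists changes from the protocol's statistical part, mentions only the confidence-interval method.

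**The concern.** Protocol 9.1.2 draws attention to patients the investigator does not see again, and the plan expects some. SAP 4.4 lists the absence of follow-up data as a deviation, and Table 14.1.3.2 prints it as a reason for exclusion from the reference set. Yet the one planned comparison of losses with completers starts after those patients have been removed.

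What is at stake is selection after enrolment. OS and PFS are analysed in the reference set (SAP 5.5), so these patients leave the survival population altogether. If they were frailer than the rest, the curves would describe a healthier group than the one enrolled. The comparison headed as a check of representativeness would not show it.

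**Working it through.** **No planned figure to reproduce.** The point rests on which patients enter a table. The documents give neither the number lost nor the number with no follow-up data.

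**Step 1: follow one patient through the rules.** Take an eligible, treated patient who is enrolled and leaves no follow-up data.
- SAP 4.3.1 removes the patient from the reference set.
- SAP 5.4.3 draws both columns of Table 14.1.4.3.3 from the reference set.
- The patient is in neither column, so the comparison contains none of these patients by definition.

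**Step 2: look for another output that fills the gap.**
- Table 14.1.3.2 counts the exclusion reason by treatment group.
- Listing 16.2.2 lists excluded patients with reasons.
- Tables 14.1.3.4 and 14.1.3.6 give drop-out reasons and end status in the safety analysis set.
- Tables 14.1.4.1.1 and 14.1.4.1.2 give age and sex for included patients and for the reference set.
- ECOG at inclusion (Table 14.1.4.1.3) is tabulated in the reference set only.

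None compares these patients with completers on ECOG, and none gives a standardised difference for them.

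**Step 3: illustrate the size.** SAP 5.4.3 gives, for a proportion,

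d = (P1 − P2) / √[(P1(1 − P1) + P2(1 − P2)) / 2].

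All counts and rates below are assumptions. Early losses are patients with no follow-up data; later losses are the others. ECOG ≥2 is a simplification, since the table reports d for each ECOG level.

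*Grid.* ECOG ≥2 is 10% in completers and 10% in later losses, so d in the reference set is 0.00. The rate among all losses is (later × 0.10 + early × rate) / (later + early). Example with 10 later and 5 early losses at 50%: (1 + 2.5)/15 = 0.233, and d = 0.133/√[(0.179 + 0.090)/2] = 0.364.

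| Early losses | ECOG ≥2 in early losses | d, 10 later losses | d, 20 later losses |
|---|---|---|---|
| 2 | 30% | 0.104 | 0.058 |
| 2 | 50% | 0.197 | 0.113 |
| 5 | 30% | 0.197 | 0.123 |
| 5 | 50% | 0.364 | 0.232 |
| 10 | 30% | 0.283 | 0.197 |
| 10 | 50% | 0.516 | 0.364 |

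The unseen share of losses runs from 2/22 = 9% to 10/20 = 50%. Two early losses never cross 0.2; five do if half of them have ECOG ≥2.

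*Direction.* Assume 15% in completers, 9 later losses and 6 early losses.
- Later 2/9, early 4/6: d = 0.19 in the reference set (2/9 against 0.15) and 0.58 with early losses added (6/15 against 0.15). The reading moves from no difference to average.
- Later 4/9, early 0/6: d = 0.68 in the reference set (4/9 against 0.15) and 0.29 with early losses added (4/15 against 0.15). Here the restriction exaggerates the difference.

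**The case against.** **The mechanism may catch few patients.** A reader might infer that everyone lost straight after the enrolment visit is deleted. The documents do not establish this. An end-of-study questionnaire is completed for patients who leave before 24 months (Protocol 5.2.2), and the case report form records last contact there. Reference-set Table 14.2.2.2.1 has a row for zero tumour assessments and does not count the inclusion visit as one. Some patients never assessed after enrolment may therefore stay in the set. This stands, and is a reason to define the term.

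**The reference set matches the survival analysis.** For asking whether censoring distorts the OS and PFS curves, it is the right population, because patients outside it are excluded rather than censored. This also stands, and the SAP nowhere presents the table as evidence that censoring is harmless. But SAP 5.4.3 is about representativeness, and a check confined to the reference set cannot show how that set was formed.

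**The clash of wording is mild.** Protocol 9.1.2 and SAP 6.1.2 are limitations text, and reference-set patients are themselves included patients. SAP 5.4.3 can be read as specifying what the others left open. Even so, it narrows the comparison without saying so in SAP 5.8.

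**Small numbers.** With 9 losses and 135 completers, the standard error of d is about √(1/9 + 1/135) = 0.34, so a value just either side of 0.2 carries little information. This is a fair limit on the table however it is populated.

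**Conclusion.** The point holds in a limited form. Eligible patients excluded for having no follow-up data cannot appear in the planned attrition comparison, and no other output compares them with completers on ECOG or by standardised difference. Selective early loss can therefore be missed.

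Two stronger readings are not supported. One is that the restriction biases the table towards no difference: the sign depends on who is lost early, as the two opposite examples show. The other is that the effect is known to be material: every count used here is assumed, and with two early losses the grid stays below the SAP's own threshold. The finding rests on the set definition and the stated population, not on any of the illustrated values.

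**What to change.** In SAP 5.4.3 and in the title of Table 14.1.4.3.3, set the population to the reference set plus included, eligible patients excluded solely for no follow-up data. Count those patients in the lost/dropped-out column or show them in a separate column; patients who died stay where SAP 5.4.3 now puts them. Define no follow-up data in SAP 4.3.1, saying whether an end-of-study form with a last-contact date counts.

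Keep patients excluded for ineligibility out of the lost column. Opening the table to all included patients would pool them with attrition, because failure to meet the inclusion criteria is a listed reason for stopping the study. The reference-set version can stay as a supplement.

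The cost is a short wording change and one rerun table. The row variables belong to the enrolment record, so no new data are needed and the OS and PFS estimates do not change. Some values will be missing: ECOG may be unknown, and SAP Table 14.1.4.1.1 allows for treatment not being stated.
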